In a single-arm, Phase II study (Study A3671008) of tremelimumab administered at 15 mg/kg every 90 days to patients with refractory melanoma, an RR of 7% and a median OS of 10 months in the second-line setting (as compared to approximately 6 months with best supportive care reported from a retrospective analysis). In a randomized, open-label, first-line Phase III study of tremelimumab (administered at 15 mg/kg every 90 days) versus chemotherapy (dacarbazine or temozolomide) in advanced melanoma (Study A3671009), results of the final analysis showed an RR of 11% and a median OS of 12.6 months in this first line setting as compared to 10.71 months with standard chemotherapy; however, these results were not statistically significant. Additionally, a Phase II maintenance study (Study A3671015) in patients with Stage IIIB or IV NSCLC who had responded or remained stable failed to achieve statistical significance. The primary endpoint of PFS at 3 months was 22.7% in the tremelimumab arm (15 mg/kg) compared with 11.9% in the best supportive care arm (Study A3671015).

Durvalumab + tremelimumab

The preclinical and clinical justification for this combination as noted in Section 1.1.4 also supports the synergy of this combination. Available data, such as those presented by [name] et al, suggest that the combination of agents targeting PD-1/PD-L1 and CTLA-4 may have profound and durable benefits in patients with melanoma. Of the 102 subjects with advanced NSCLC treated with durvalumab in combination with tremelimumab in Study

D4190C00006, 63 subjects with at least 16 weeks of follow-up were evaluable for response (defined as measurable disease at baseline and at least 1 follow-up scan; this included discontinuations due to disease progression or death without follow-up scan). Of the 63 evaluable subjects, 17 (27%) had a best overall response of PR, 14 (22%) had SD, 22 (35%) had PD, and 10 (16%) were not evaluable. The ORR (confirmed and unconfirmed CR or PR) was 27% and the DCR (CR, PR, or SD) was 49% as assessed by RECIST v1.1.

Current experience with single-agent IMT studies suggests that clinical responses may be restricted to a subset of any given patient population and that it might be beneficial to enrich the patient population by selecting patients likely to respond to therapy. To date, no assay has been established or validated, and no single approach has proven accurate, for patient enrichment for IMTs. However, independent data from multiple sources using different assays and scoring methods suggests that PD-L1 expression on tumor cells and/or tumor infiltrating cells may be associated with greater clinical benefit.

Data from ongoing studies with durvalumab and other agents targeting the PD-1/PD-L1 pathway suggest, as shown in a number of tumor types (e.g., NSCLC, renal cell carcinoma, and melanoma), that monotherapy may be more efficacious (in terms of ORR) in patients who are PD-L1-positive.

Date:

Given these findings, a number of ongoing studies are assessing the activity of agents in patients with PD-L1–positive tumors. There is also an unmet medical need in patients with PD-L1–negative tumors that needs to be addressed. Data, as of 27 January 2015 from Study 006 show that with the addition of tremelimumab to durvalumab, the ORR can be increased to 25% in patients with PD-L1 negative NSCLC. As patients with PD-L1 positive disease can also have an increase in ORR, from 25% with durvalumab monotherapy, to 36% with the combination of durvalumab and tremelimumab, the study will enroll all patients with NSCLC, with an emphasis on those determined to be PD-L1 negative.

Potential risks

Potential risks, based on the mechanism of action of durvalumab and related molecules, include immune-mediated reactions, such as colitis, pneumonitis, hepatitis/hepatotoxicity, neuropathy/neuromuscular toxicity, endocrinopathy, dermatitis, pancreatitis and nephritis. Additional important potential risks include infusion related reactions, hypersensitivity, anaphylaxis or serious allergic reactions, serious infections, and immune complex disease.

Study CD-ON-durvalumab-1108: The safety profile of durvalumab monotherapy in the 694 subjects with advanced solid tumors treated at 10 mg/kg Q2W in Study CD-ON-durvalumab-1108 has been broadly consistent with that of the overall 1,279 subjects who have received durvalumab monotherapy (not including subjects treated with blinded investigational product) across the clinical development program. The majority of treatment related AEs were manageable with dose delays, symptomatic treatment, and in the case of events suspected to have an immune basis, the use of established treatment guidelines for immune-mediated toxicity. As of 07May2015, among the 694 subjects treated with durvalumab 10 mg/kg Q2W in Study CD-ON-durvalumab-1108, a total of 378 subjects (54.5%) experienced a treatment-related AE, with the most frequent (occurring in $\geq 5\%$ of subjects) being fatigue (17.7%), nausea (8.6%), diarrhea (7.3%), decreased appetite (6.8%), pruritus (6.3%), rash (6.1%), and vomiting (5.0%). A majority of the treatment related AEs were Grade 1 or Grade 2 in severity with \geq Grade 3 events occurring in 65 subjects (9.4%). Treatment related \geq Grade 3 events reported in 3 or more subjects ($\geq 0.4\%$) were fatigue (12 subjects, 1.7%); increased aspartate aminotransferase (AST; 7 subjects, 1.0%); increased gamma-glutamyltransferase (GGT; 6 subjects, 0.9%); increased alanine aminotransferase (ALT; 5 subjects, 0.7%); and colitis, vomiting, decreased appetite, and hyponatremia (3 subjects, 0.4% each). Six subjects had treatment related Grade 4 AEs (upper gastrointestinal hemorrhage, increased AST, dyspnea, neutropenia, colitis, diarrhea, and pneumonitis) and 1 subject had a treatment-related Grade 5 event (pneumonia). Treatment related serious adverse events (SAEs) that occurred in ≥ 2 subjects were colitis and pneumonitis (3 subjects each). A majority of the treatment-related SAEs were \geq Grade 3 in severity and resolved with or without sequelae. AEs that resulted in permanent discontinuation of durvalumab were considered as treatment related in 18 subjects (2.6%), with colitis being the most frequent treatment-related AE resulting in discontinuation (3 subjects). A majority of the treatment related AEs resulting in discontinuation of durvalumab were \geq Grade 3 in severity and resolved with or without sequelae.

Study D4191C00003/ATLANTIC: The safety profile of durvalumab monotherapy in Study CD-ON-durvalumab-1108 is generally consistent with that of Study D4191C00003/ATLANTIC in subjects with locally advanced or metastatic non-small-cell lung cancer (NSCLC) treated with

Date:

durvalumab 10 mg/kg Q2W. As of 05May2015, 264 of 303 subjects (87.1%) reported any AE in Study D4191C00003/ATLANTIC. Overall, events reported in $\geq 10\%$ of subjects were dyspnea (18.8%), fatigue (17.8%), decreased appetite (17.5%), cough (14.2%), pyrexia (12.2%), asthenia (11.9%), and nausea (11.2%). Nearly two thirds of the subjects experienced AEs that were Grade 1 or 2 in severity and manageable by general treatment guidelines as described in the current durvalumab study protocols. Grade 3 or higher AEs were reported in 107 of 303 subjects (35.3%). A total of 128 subjects (42.2%) reported AEs that were considered by the investigator as related to investigational product. Treatment related AEs (all grades) reported in $\geq 2\%$ of subjects were decreased appetite (6.6%); fatigue (5.9%); asthenia (5.0%); nausea (4.6%); pruritus (4.3%); diarrhea, hyperthyroidism, hypothyroidism, and pyrexia (3.3% each); rash (2.6%); weight decreased (2.3%); and vomiting (2.0%). Treatment related Grade 3 AEs reported in ≥ 2 subjects were pneumonitis (3 subjects) and increased GGT (2 subjects). There was no treatment related Grade 4 or 5 AEs. Ninety-four of 303 subjects (31.0%) reported any SAE. SAEs that occurred in $\geq 1.0\%$ of subjects were dyspnea (6.6%); pleural effusion, general physical health deterioration (2.3% each); pneumonia (2.0%); hemoptysis, pulmonary embolism (1.3% each); and pneumonitis, respiratory failure, disease progression (1.0% each). Nine subjects had an SAE considered by the investigator as related to durvalumab. Each treatment related SAE occurred in 1 subject each with the exception of pneumonitis, which occurred in 3 subjects. Fifteen of 303 subjects (5.0%) have died due to an AE (pneumonia [3 subjects]; general physical health deterioration, disease progression, hemoptysis, dyspnea [2 subjects each]; pulmonary sepsis, respiratory distress, cardiopulmonary arrest [verbatim term (VT)], hepatic failure, and sepsis [1 subject each]). None of these events was considered related to durvalumab. Twenty-three of 303 subjects (7.6%) permanently discontinued durvalumab treatment due to AEs. Events that led to discontinuation of durvalumab in ≥ 2 subjects were dyspnea, general physical health deterioration, and pneumonia. Treatment-related AEs that led to discontinuation were increased ALT and increased hepatic enzyme, which occurred in 1 subject each.

Tremelimumab

Potential risks, based on the mechanism of action of tremelimumab and related molecules (ipilimumab) include potentially immune-mediated gastrointestinal (GI) events including enterocolitis, intestinal perforation, abdominal pain, dehydration, nausea and vomiting, and decreased appetite (anorexia); dermatitis including urticaria, skin exfoliation, and dry skin; endocrinopathies including hypophysitis, adrenal insufficiency, and hyperthyroidism and hypothyroidism; hepatitis including autoimmune hepatitis and increased serum ALT and AST; pancreatitis including autoimmune pancreatitis and lipase and amylase elevation; respiratory tract events including pneumonitis and interstitial lung disease (ILD); nervous system events including encephalitis, peripheral motor and sensory neuropathies, and Guillain-Barré syndrome; cytopenias including thrombocytopenia, anemia, and neutropenia; infusion-related reactions; anaphylaxis; and serious allergic reactions. The profile of AEs and the spectrum of event severity have remained stable across the tremelimumab clinical program and are consistent with the pharmacology of the target. To date, no tumor type or stage appears to be associated with unique AEs (except for vitiligo that appears to be confined to patients with melanoma). Overall, 944 of the 973 patients (97.0%) treated with tremelimumab monotherapy as of the data cutoff date of 1 November 2015 (for all studies except D4190C00006 that has a cutoff date of 15Apr2015 and not including 497 patients who have been treated in the

Date:

ongoing blinded Phase IIb Study D4880C00003) experienced at least 1 AE. The events that resulted in discontinuation of tremelimumab in 10.0% of patients, were serious in 36.5%, were Grade ≥ 3 in severity in 49.8%, were fatal in 67.7%, and were considered to be treatment related in 79.1% of patients. The frequency of any AEs and Grade ≥ 3 AEs was generally similar across the tremelimumab dose groups. However, a higher percentage of patients in the 10 mg/kg every 28 days and 15 mg/kg every 90 days groups compared with the All Doses <10 mg/kg group experienced treatment-related AEs, SAEs, AEs resulting in discontinuation of investigational product (IP), and deaths.

No safety studies in animals have been performed combining tremelimumab with durvalumab. As both CTLA-4 and PD-L1 have mechanisms of actions that enhance activation of immune cells, their potential to induce cytokine release was tested in a whole-blood assay system. Durvalumab and tremelimumab, either alone or in combination, did not induce cytokine release in blood from any donor.

Study D4190C00006: The safety profile of durvalumab and tremelimumab combination therapy in the 102 subjects with advanced NSCLC in Study D4190C00006 is generally consistent with that observed across 177 subjects treated with durvalumab and tremelimumab combination therapy (not including subjects treated with blinded investigational product). As of 15Apr2015, 95 of 102 subjects (93.1%) reported at least 1 AE. All subjects in the tremelimumab 3 and 10 mg/kg dose cohorts experienced AEs; subjects in the durvalumab 20 mg/kg and tremelimumab 1 mg/kg Q4W cohort experienced the lowest AE rate (77.8%). Treatment-related AEs were reported in 74 of 102 subjects (72.6%), with events occurring in > 10% of subjects being diarrhea (27.5%), fatigue (22.5%), increased amylase and pruritus (14.7% each), rash (12.7%), colitis (11.8%), and increased lipase (10.8%). Treatment-related \geq Grade 3 AEs reported in \geq 5% of subjects were colitis (8.8%), diarrhea (7.8%), and increased lipase (5.9%). Five subjects reported treatment-related Grade 4 events (sepsis, increased ALT, and increased AST in 1 subject; increased amylase in 2 subjects; myasthenia gravis in 1 subject; and pericardial effusion in 1 subject) and 2 subjects had treatment-related Grade 5 events (polymyositis and an uncoded event of neuromuscular disorder [VT]); the Grade 4 event of myasthenia gravis and Grade 5 polymyositis occurred in 1 subject. There were 2 subjects (both in the MEDI4736 20 mg/kg + tremelimumab 3 mg/kg Q4W cohort) with dose-limiting toxicities (DLTs): 1 subject with Grade 3 increased AST, and 1 subject with Grade 3 increased amylase and Grade 4 increased lipase. Fifty-six subjects (54.9%) reported SAEs, with events occurring in > 5% of subjects being colitis (9.8%) and diarrhea (7.8%). Thirty-six subjects (35.3%) experienced treatment-related SAEs. Twenty-seven subjects (26.5%) permanently discontinued treatment due to AEs. Treatment-related AEs resulting in discontinuation in \geq 2 subjects were colitis (7 subjects), pneumonitis (5 subjects), diarrhea (3 subjects), and increased AST (2 subjects). Additional safety results from this study are presented in the durvalumab and tremelimumab IBs.

In the literature, using the combination of the same class of drugs (e.g., anti-PD-1 and anti-CTLA4 antibodies), specifically nivolumab + ipilimumab in a study involving patients with malignant melanoma, the safety profile of this combination had shown occurrences of AEs assessed by the Investigator as treatment-related in 93% of treated patients, with the most frequent events being rash (55% of patients), pruritus (47% of patients), fatigue (38% of patients), and diarrhea (34% of patients). Grade 3 or 4 AEs, regardless of causality, were

Date:

noted in 72% of patients, with Grade 3 or 4 events assessed by the Investigator as treatment-related in 53%. The most frequent of these Grade 3 or 4 events assessed by the Investigator as treatment-related include increased lipase (in 13% of patients), AST (in 13%), and ALT levels (in 11%). Frequent Grade 3 or 4 selected AEs assessed by the Investigator as treatment-related in the combination therapy included hepatic events (in 15% of patients), GI events (in 9%), and renal events (in 6%). Isolated cases of pneumonitis and uveitis were also observed.

Fixed Dosing for durvalumab and tremelimumab

A population PK model was developed for durvalumab using monotherapy data from a Phase 1 study (study 1108; N=292; doses= 0.1 to 10 mg/kg Q2W or 15 mg/kg Q3W; solid tumors). Population PK analysis indicated only minor impact of body weight (WT) on PK of durvalumab (coefficient of ≤ 0.5). The impact of body WT-based (10 mg/kg Q2W) and fixed dosing (750 mg Q2W) of durvalumab was evaluated by comparing predicted steady state PK concentrations (5th, median and 95th percentiles) using the population PK model. A fixed dose of 750 mg was selected to approximate 10 mg/kg (based on median body WT of ~75 kg). A total of 1000 patients were simulated using body WT distribution of 40–120 kg. Simulation results demonstrate that body WT-based and fixed dosing regimens yield similar median steady state PK concentrations with slightly less overall between-subject variability with fixed dosing regimen.

Similarly, a population PK model was developed for tremelimumab using data from Phase 1 through Phase 3 (N=654; doses= 0.01 to 15 mg/kg Q4W or Q90D; metastatic melanoma) [Wang et al. 2014]. Population PK model indicated minor impact of body WT on PK of tremelimumab (coefficient of ≤ 0.5). The WT-based (1 mg/kg Q4W) and fixed dosing (75 mg/kg Q4W; based on median body WT of ~75 kg) regimens were compared using predicted PK concentrations (5th, median and 95th percentiles) using population PK model in a simulated population of 1000 patients with body weight distribution of 40 to 120 kg. Similar to durvalumab, simulations indicated that both body WT-based and fixed dosing regimens of tremelimumab yield similar median steady state PK concentrations with slightly less between-subject variability with fixed dosing regimen.

Similar findings have been reported by others [Ng et al 2006, Wang et al. 2009, Zhang et al, 2012, Narwal et al 2013]. Wang and colleagues investigated 12 monoclonal antibodies and found that fixed and body size-based dosing perform similarly, with fixed dosing being better for 7 of 12 antibodies. In addition, they investigated 18 therapeutic proteins and peptides and showed that fixed dosing performed better for 12 of 18 in terms of reducing the between-subject variability in pharmacokinetic/pharmacodynamics parameters [Zhang et al 2012].

A fixed dosing approach is preferred by the prescribing community due to ease of use and reduced dosing errors. Given expectation of similar pharmacokinetic exposure and variability, we considered it feasible to switch to fixed dosing regimens. Based on average body WT of 75 kg, a fixed dose of 1500 mg Q4W durvalumab (equivalent to 20 mg/kg Q4W) and 75 mg Q4W tremelimumab (equivalent to 1 mg/kg Q4W) is included in the current study.

Date:

Fixed dosing of durvalumab and tremelimumab is recommended only for subjects with > 30kg body weight due to endotoxin exposure. Patients with a body weight less than or equal to 30 kg should be dosed using a weight-based dosing schedule.

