
2.1 OBJECTIVES AND SCIENTIFIC AIMS

Primary Endpoints:

- Determine the effectiveness of the each arm by measuring Overall Response Rate [ORR = Complete Response (CR) + Partial Response (PR)] by RECIST v 1.1
- Determine Progression Free Survival (PFS) rate in each arm at 24 weeks (+/- 1 week)

- **Secondary Endpoints**

- Overall response rate in each arm evaluated by Immune-related Response Criteria in Solid Tumors (irRECIST) criteria. irRECIST assessments will only be completed for patients continuing treatment beyond PD
- Clinical benefit (CR + PR + Stable Disease [SD]) rate in each arm by 24 weeks +/- 7 days Duration of response in each arm
- Determine the rate of immune-related Adverse Events (irAE)
- Determine the rate of serious adverse events (SAE)
- Establish safety of each arm

Exploratory Endpoints:

- Determine the ability of the laboratory parameters to predict clinical benefit:
 - Archival tumor tissue PD-L1 expression IHC
 - Archival tumor tissue immune-related gene expression profiles
 - Archival tumor tissue IHC
 - Peripheral blood immune phenotyping
 - Peripheral blood gene expression profiling
 - Peripheral blood T cell receptor repertoire

Date:

- Peripheral blood serologic responses

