The Cancer Genome Atlas (TCGA) recently reported on the genomic, transcriptomic, and proteomic analysis of 373 endometrial carcinomas using massively parallel sequencing and array-based technologies, in combination with DNA methylation, reverse-phase protein array, and microsatellite instability analyses.(Kandoth, 2013) Based on the integration of the somatic gene mutations, microsatellite instability, and somatic copy-number alterations results, endometrial carcinomas were categorized into four genomic groups: (1) A group of 'ultramutated' tumors characterized by very high mutation rates, all harboring mutations in the exonuclease domain of the polymerase epsilon (POLE) gene; (2) A 'hypermutated' group of endometrial carcinomas characterized by microsatellite instability due to MLH1 promoter methylation, with high mutation rates and few copy-number alterations; (3) A 'copynumber low' group comprised of most of the microsatellite stable grade 1 and grade 2 endometrioid carcinomas with low mutation rates; and (4) A group of 'copy-number high' tumors with extensive copy number aberrations, low mutation rates, and recurrent TP53 mutations comprised of serous carcinomas and 25% of FIGO (International Federation of Gynecology and Obstetrics) grade 3 endometrioid adenocarcinomas. With regards to clinical outcome, ultramutated endometrial carcinomas with POLE exonuclease domain mutations had a favorable progression free survival as compared with the other three TCGA genomic groups. (Kandoth, 2013) It has been suggested that hypermutated tumors may harbor more tumor specific neoantigens and increased amounts of TILs. Therefore, an assessment of whether POLE and MSI ECs harbor more neoantigens and TILs than the comparatively hypomutated microsatellite-stable (MSS) ECs was performed. Prediction of neoantigen load was performed using sequencing data from the Cancer Genome Atlas data set. Evaluation of tumor-infiltrating lymphocytes (TILs) and PD-1 and PD-L1 expression was performed in 63 patients with EC referred to our institution. The predicted median (range) neoantigen load (predicted neopeptides per sample) was proportional to the mutational load: highest in ultramutated polymerase e (POLE) tumors (8342 [628-20 440]), less in hypermutated MSI (541 [146-8063]; $P < .001$), and lowest in microsatellite-stable tumors (70.5 [7-1877]; $P < .001$). The POLE and MSI ECs exhibited higher numbers of CD3+ (44.5 vs 21.8; $P = .001$) and CD8+ (32.8 vs 13.5; $P < .001$) TILs compared with microsatellite-stable tumors.

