
Date:

PD-1 was overexpressed in TILs (81% vs 28%; $P < .001$) and peritumoral lymphocytes (90% vs 28%; $P < .001$) of POLE and MSI tumors. PD-L1 expression was infrequently noted in tumor cells but was common in intraepithelial immune cells and more frequent in POLE and MSI tumors (39% vs 13%; $P = .02$). (Howitt, 2015)

Taken together, we believe that this data provides abundant rationale to investigate the efficacy of the anti-PD-L1 agent durvalumab with or without the anti-CTLA4 agent tremelimumab in patients with advanced/recurrent endometrial malignancies. At this time, there is tremendous interest in evaluating immune check-point inhibitors in advanced endometrial cancers.

Rationale for combining Durvalumab and Tremelimumab in Endometrial Carcinomas

There is sound rationale for evaluating the combination of durvalumab and tremelimumab for the treatment of advanced endometrial carcinomas. Firstly, the mechanisms of activation of known sites for activity of CTLA-4 and PD-1 are non-redundant, suggesting that targeting both pathways may have additive or synergistic activity. Secondly, preclinical data in mouse models of transplantable solid tumors, and clinical data emerging from studies in melanoma supports the superior anti-tumor activity of combination therapy over monotherapy, albeit at increased toxicity (Larkin, 2015 #9006). Based upon these observations, combination therapy may generate superior anti-tumor activity, which may translate into higher rates of response in tumors. However, as yet, it is not known whether combination therapy will result in superior activity in comparison to single agent durvalumab in endometrial cancer and whether the combination will be safe in this patient population.

For this study, we hypothesize that durvalumab plus tremelimumab will be well tolerated and will be associated with higher efficacy than the durvalumab alone in patients with advanced endometrial cancer and endometrial carcinosarcoma.

Efficacy Data

Durvalumab

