Exploratory objectives: For exploratory biomarker analyses, patients will be dichotomized on the basis of clinical benefit (CBR) rate (CR+PR+SD) as the outcome measure. Exploratory endpoints will be analyzed by treatment arm. All biomarkers without known cutoffs will be treated as continuous variables. For tissue based biomarkers, CBR will be correlated to the level of tissue expression of PD-L1 (binary: positive vs negative), or specific genes/gene signatures identified from transcriptional profiling. Non parametric 2 sample tests will be used to assess differences in the distribution of markers between the 2 groups (responders vs non responders). Archival tumor tissue IHC will be assessed only at baseline while other markers will be assessed at baseline and during treatment and their change from baseline will be analyzed. For markers such as number of infiltrating CD8+ cells and change in ICOS level expression on lymphocytes from baseline levels, we do not have established cutoffs, thus we will examine them as continuous variables. In these biomarkers we will look at changes from baseline to treatment (focused on early changes or changes within 8-12 weeks), and we explore these changes graphically in order to assess potential relationships between responders and non responders.

Date:

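### The biomarker analysis takes no account of MSI status, so it cannot show whether a tissue marker adds to MSI status or works in patients who are not MSI-high

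*Combined protocol and SAP*

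**What the plan says.** Section 3.0 (Immune checkpoint inhibition in endometrial carcinomas) summarises a 63-patient study comparing POLE and MSI tumours with microsatellite-stable ones. It says "The POLE and MSI ECs exhibited higher numbers of CD3"-positive cells (44.5 against 21.8) and of CD8-positive cells (32.8 against 13.5). PD-1 in infiltrating lymphocytes was 81% against 28%. On PD-L1 it says "PD-L1 expression was infrequently noted in tumor cells but was common in intraepithelial immune cells and more frequent in POLE and MSI tumors" (39% against 13%).

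The exploratory objective in section 2.1 reads "Determine the ability of the laboratory parameters to predict clinical benefit". Sections 12.5.1 and 12.5.2 measure tissue PD-L1, CD8 infiltration and PD-1 on archival tumour.

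For the analysis, section 14.0 (Exploratory objectives) says "For exploratory biomarker analyses, patients will be dichotomized on the basis of clinical benefit (CBR) rate (CR+PR+SD) as the outcome measure", and then "Non parametric 2 sample tests will be used to assess differences in the distribution of markers between the 2 groups". The only subdivision it names is treatment arm. It gives no covariate, stratified test or subgroup for MSI or POLE status.

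MSI enters the design only through randomization (sections 4.2 and 15.3). Stratum 1 pools MSI-high carcinoma with carcinosarcoma and is capped at 10 patients per arm. POLE is not mentioned after the background.

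**The concern.** The marker comparison is made within an arm, between patients who benefit and patients who do not. Stratified randomization balances the arms against each other and does nothing for this comparison. If MSI-high patients benefit more often, they are over-represented in the benefit group, and any marker that is higher in MSI-high tumours will tend to be higher there too, even if it says nothing about benefit once MSI status is known.

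At stake is what a positive CD8, PD-1 or PD-L1 result would mean. MSI-high status is determined for each patient at randomization. A marker that only restates it offers nothing new, and may not help select among patients who are not MSI-high. The planned tests cannot separate these two situations.

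**Working it through.** **The plan's own figures.** The documents give no power or error rate for the biomarker analyses, so there is none to reproduce. The efficacy figures do reproduce. The ORR rule (at least 3 of 27, then at least 7 of 40; 10% against 25%) has exact type I error 0.098 and power 0.900. The PFS rule (at least 10 of 40; 15% against 35%) gives 0.067 and 0.936. Nothing below touches them.

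**Inputs from the documents.** 40 patients per arm; stratum 1 at most 10 per arm, so MSI-high is at most 10/40 = 25% of a 40-patient arm and at least 30/40 = 75% are not MSI-high; PD-L1 39% against 13%; CD8 32.8 against 13.5.

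**Assumptions.** Benefit rates by MSI/POLE status; the number of such patients per arm; the spread of CD8 (no SD is given, so a log-normal with coefficient of variation 0.6 to 1.0). The two CD8 figures are treated as means.

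**Binary PD-L1.** Let q be the MSI/POLE share, with no link between PD-L1 and benefit inside either group. Take q = 0.25 and benefit 60% against 30%:

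- PD-L1 positive: 0.25 × 0.39 + 0.75 × 0.13 = 0.195.
- Benefit if positive: (0.0975 × 0.60 + 0.0975 × 0.30) / 0.195 = 0.450.
- Benefit if negative: (0.25 × 0.61 × 0.60 + 0.75 × 0.87 × 0.30) / 0.805 = 0.357.
- Crude odds ratio: (0.450/0.550) / (0.357/0.643) = 1.48, against a true within-group value of 1.

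The last column is the exact chance that a two-sided 5% Fisher test in one 40-patient arm is significant in the positive direction.

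| Benefit, MSI/POLE v other (q = 0.25) | Crude OR | Significant positive |
|---|---|---|
| 35% v 35% | 1.00 | 1.7% |
| 50% v 35% | 1.21 | 2.9% |
| 60% v 30% | 1.48 | 4.9% |
| 70% v 25% | 1.79 | 8.0% |
| 80% v 20% | 2.19 | 12.3% |

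Over shares of 12.5% to 50%, whenever benefit differs, the odds ratio is 1.14 to 2.32 and the chance 2.4% to 14.2%. Shares above 25% would need POLE tumours outside stratum 1.

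**CD8-like continuous marker.** Simulated arms of 40 with 5, 8 or 10 MSI/POLE patients, a log-normal marker with means 32.8 and 13.5, and no marker effect within either group. The plain Wilcoxon test is compared with the van Elteren test (Wilcoxon stratified by MSI/POLE status), both two-sided at 5%.

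| Setting | Plain test rejects | Stratified test rejects |
|---|---|---|
| Equal benefit, 35% v 35% | about 5% | about 5% |
| 8 patients, 65% v 30% | about 10-15% | about 5% |
| 5-10 patients, 55-70% v 25-30% | about 6-30% | about 5% |

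Nearly all the excess rejections point the same way: high marker, more benefit.

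**The case against.** **The driver is assumed.** No passage gives benefit by MSI or POLE status under checkpoint inhibition. The background reports only favourable progression-free survival for POLE tumours, not under these drugs. With equal benefit there is no distortion, and at 45% against 30% the plain CD8 test rejects in only 5.8-7.0% of arms. This stands. The gap is plausible on the protocol's own rationale, but it is not documented.

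**The stated aim is prediction.** If MSI-high patients have both more CD8 and more benefit, CD8 does predict benefit in this population. A reader might infer that the extra rejections are false positives for the stated objective. The documents do not support that: the objective does not ask for value beyond MSI status. What is missing is an analysis of incremental value.

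**POLE status is not shown to be known.** A reader might infer from the required genomic profiling (section 6.2, criterion 12) that it is. The documents mention only immunohistochemistry, MSI testing and mismatch-repair mutations, and do not say whether the assay reports POLE.

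**Reach is limited.** The background data concern tumour tissue. They say nothing about the blood markers, which are largely analysed as change from baseline. Transfer of the PD-L1 figures is uncertain too: section 12.5.1 scores tumour and immune cells, and positivity is not defined.

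**Consequences are small.** The analyses are exploratory, and an MSI-adjusted look could be added at reporting. That is true, but specifying it beforehand costs little and avoids choosing it after the results are seen.

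**Conclusion.** The point holds as a gap in the exploratory analysis. For baseline tissue markers that track MSI/POLE status in the protocol's own background, the planned tests cannot distinguish a marker that informs beyond MSI status from one that only tags it.

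The size depends on an undocumented benefit gap. Over assumed benefit of 55-70% against 25-30%, a CD8-like marker with no effect of its own is significant in about 6-30% of arms. Binary PD-L1 is significant and positive in about 2-14% over a wider set of assumptions. Both fall to their null rates (about 5% and 1.7%) if benefit is equal.

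A reader might infer that such a marker will appear to predict benefit. These figures do not support that: even at the upper end, about 70% of arms would show nothing significant for CD8. The ORR and PFS rules are untouched, so this is an inexpensive improvement and not a threat to the trial's main conclusions.

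**What to change.** In section 14.0 (Exploratory objectives), keep the planned unstratified tests and add, for the baseline tumour-tissue markers:

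1. A test stratified by MSI-high status: van Elteren for continuous markers, an exact stratified test for binary PD-L1.
2. Each marker's AUC with a confidence interval in patients who are not MSI-high.

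Record MSI-high separately from carcinosarcoma. The randomization stratum pools the two, so adjusting for it would not serve. Add POLE status only if the required sequencing reports it.

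Section 12.5.2 dichotomizes patients on the primary efficacy endpoint, whereas section 14.0 uses clinical benefit. Settle which applies in the same edit; the argument is the same for either.

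The cost is a few sentences and some analysis code, with no new samples, since MSI status is already determined for randomization. Cells will be small, with at most 10 MSI-high patients per arm, so results should be labelled exploratory. The stratified test has essentially no power for a marker that acts only through MSI status, which is why the unstratified result should stay beside it.
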